3.3 Study Duration and Dates

The duration of participation of each patient in the study will be approximately 10 days and will include: screening and randomization (1 day), study treatment (7 days, including the day of randomization), follow-up (3 days).

The first part of the study started on 09 November 2016 (First Visit First Patient) and it has been completed on 27 April 2017 (Last Visit Last Patient). For the second part of the study the start of patient enrollment is expected in November, 2017 and the completion of the study visits in February 2018.

3.3.1 Preclinical Trials

Investigational studies of general toxicity (acute, subacute, chronic) of finished pharmaceutical form of Levopront® have shown that the drug at acute and chronic experimental conditions (3 months) does not exhibit toxic effects in warm-blooded laboratory animals (rodent and non-rodent species – rabbits), including at the stage of development. It is of note that planning and conduct of the study strictly met Russian MoH requirements and international standards in the field of preclinical study of safety of new pharmacological drugs – GLP (Good Laboratory Practice).

Results of toxicometry, data of observations of test animals in postintoxication period of acute poisoning, and necropsy data suggest that Levopront (Levodropropizine syrup) belongs to class VI of relatively innocuous drugs (H. Hodge et al. *Clinical Toxicology of Commercial Products. Acute Poisoning*. Ed. IV, Baltimore, 1975, 427 p.; K.K. Sidorov, 1973).

Condition of animals after acute intoxication suggests its good tolerability at doses exceeding human therapeutic doses (approximately 0.5 mL/kg) by several ten-fold.

Subacute (30 days) daily intragastric administration of Levopront in sexually immature animals (rats, rabbits) and chronic (90 days) daily intragastric administration of Levopront in mature animals (rats, rabbits) had not harmful effects on the key adaptive systems (nervous, cardiovascular, hematopoietic, excretory, respiratory), metabolism, general condition and development, key hemostatic body parameters.

A lack of irritating effects on GI tissues should also be noted. It applies both to rodent and non-rodent species, suggesting of universal nature of innocuous properties of the drug.

The drug has shown to be free of allergenic potential.

According to Classification of hazardous drugs for clinical use ($SI > 5$) Levopront® belongs to class III of low toxic (low hazardous) drugs.

Results of Levopront® toxicity tests in sexually immature animals supported its safety in pediatric population.

Key pharmacokinetic parameters were defined, and analysis of pharmacokinetic response after oral administration of Levopront® to dogs was performed. No evidence of drug accumulation in the body and possible cumulative effects were observed.

Results of investigation of safety of Levopront (Dompe farmaceutici S.p.A., Italy) support low toxicity of the drug both in adult and pediatric populations.

3.3.2 Clinical Trials

Efficacy:

The administration of levodropropizine has been associated in all studies with a statistically significant decrease in cough starting from the first day of treatment, a finding that confirms that results may not be attributed to the natural course of the disease.

Moreover, the observed statistically and clinically significant reduction in the number of cough-related night awakenings following levodropropizine treatment should translate into a better quality of life, both in children and in adults, particularly in neoplastic patients.

The magnitude of the drug's antitussive effect has been shown to be superimposable among the different underlying disease groups. This represents an advantage for the drug since use is not to be limited to specific etiologic diseases with non-productive cough, but can be extended to any lower and upper respiratory tract diseases, to cough associated with asthma, neoplasia, whooping cough (pertussis), cardiac cough, and can also be used in the prevention of cough during and after surgical interventions or fiberbronchoscopy.

Types of diseases covered in the conducted trials can be considered representative of those present in the population that will receive cough-suppressing agents in clinical practice.

Controlled studies, both placebo- and active-control, have shown levodropropizine to be more active than placebo and equally effective than tested reference drugs (i.e. dextromethorphan, clobutinol, dropropizine; dihydrocodeine, cloperastine and morclofone) in reducing the frequency of cough as measured by the number of coughing spells in the post-treatment period in adult patients. Levodropropizine was also shown to be clinically as effective as dihydrocodeine in reducing the cough associated with thoracic neoplasia (particularly persistent, invalidating cough, resistant even to radiotherapy).

In children, efficacy has been demonstrated both in a dose-finding study and in comparative and/or open-label clinical studies on a total of 608 subjects receiving levodropropizine.

Finally, the results of a meta-analysis, carried out on an ITT sample rigorously selected across trials, and through appropriate patient stratifications, have confirmed the lack of influence of cough etiology or patients age on the efficacy of the medication.

The level of clinical efficacy and substantial benefit from levodropropizine treatment has been recognized by the reference medical community and this is reflected in the article "Cough Suppressant and Pharmacologic Protussive Therapy: ACCP Evidence-Based Clinical Practice Guidelines" published in Chest (Bolser, 2006), where the drug is recommended as the treatment of choice, amongst the peripheral cough suppressants, for the short-term symptomatic relief of cough in patients with chronic or acute bronchitis.

Safety:

The safety of levodropropizine has been studied in clinical pharmacology and clinical studies comprising 107 healthy volunteers and 2868 patients, 788 of whom were under 14 years of age.

Out of the 2868 subjects exposed to 1-22 days of levodropropizine in clinical studies, suspected ADRs have been reported in as few as 60 patients (2.1%) without any excess risk for paediatric patients.

Amongst the reported ADRs, CNS effects, such as cephalalgia, somnolence, fatiguability/asthenia accounted for 25 events (0.9%); gastrointestinal events, such as nausea, diarrhoea, abdominal cramps, pyrosis/dyspepsia, gastralgia and vomiting for 31 events (1.1%). In 1 case dyspnea was reported, but the relationship to levodropropizine administration was not assessed.

Allergic reactions were evident in 7 cases. Cardiovascular organ system was involved in 3 cases with palpitations and in 1 case with precordial pain; in none of these cases was a relationship to study drug considered.

Tolerability data from clinical studies confirm results from animal experiments with regard to the lack of CNS effects of levodropropizine. Indeed, no changes in the EEG pattern or significant modifications of the psychomotor performance have been observed. Comparative clinical studies have shown that the frequency of somnolence reported with the reference drugs (dihydrocodeine, dextromethorphan, clobutinol, dropropizine) was more than double that reported with levodropropizine, and at times statistically significant

Neither age nor concomitant therapies did modify the safety profile, even when benzodiazepines were concomitantly administered (Bejor et al., 1988; Arrigo et al., 1988; Bejor et al., 1990; Fiocchi et al., 1989; 1991).

As levodropropizine does not interfere with the respiratory center and with the clearance capacity of the lung, drug administration can be considered safe also in patients with severe respiratory insufficiency (Bossi et al., 1988).

Results from special population studies, such as mild to moderate renal impaired and hepatic impaired patients, do not contraindicate the use of levodropropizine in such patients. Post marketing studies and spontaneous reporting confirmed the frequency and type of AEs observed in clinical trials.

3.3.3 Risk/Benefit Analysis

This study is aimed at collecting data on efficacy and safety of Levopront® in patients with acute non-productive cough associated with acute respiratory infection of upper airways. It is suggested that study subjects receiving Levopront® for 7 days could be achieved a high frequency resolution of cough due to stimulation of peripheral ends of sensitive nerves and modulation of neuropeptides involved into the cough reflex.

According to results of previous preclinical trials, Levopront® was free of allergenic, immunotoxic, cancerogenic, mutagenic potential, did not affect respiratory, cardiovascular, urinary system, blood hematology and biochemistry parameters.

Preclinical studies have shown that the drug, both in terms of acute administration, and prolonged use for 3 months did not have a toxic effect on the body of warm-blooded laboratory animals (rodents and non-rodents - rabbits), including on growing organisms.

In bioequivalence studies of two pharmaceutical forms of levodropropizine, the drug demonstrated good tolerability and safety at single doses.

Efficacy and safety of levodropropizine was also evidenced in multiple Phase II and III trials, including studies in pediatric populations.

3.3.4 Significant Potential Risks

Levopront® is a drug of Dompe Farmaceutici S.p.A., Italy, authorized in European Union and in extra European countries (Brazil, Mexico, Chile Columbia, Costa Rica, Ecuador, El Salvador, Guatemala, Honduras, Indonesia, Nicaragua, Panama, Philippines, Thailand, Venezuela, Turkey, South Korea), and established within the past two decades as a reliable and safe cough agent. Potential risks (known side effects) of Levopront® include:

Eye disorders: Mydriasis, bilateral blindness.

Immune system disorders: Allergic and anaphylactoid reactions, eyelid edema, angioneurotic edema, urticaria.

Psychiatric disorders: Nervousness, drowsiness, personality change, or personality disorder.

Nervous system disorders: Syncope, dizziness, vertigo, tremor, paraesthesia, tonic-clonic seizures and attacks of petit mal, hypoglycemic coma.

Cardiac disorders: Palpitations, tachycardia, atrial bigeminy.

Vascular disorders: Hypotension.

Respiratory, thoracic and mediastinal disorders: Dyspnea, cough, edema of the respiratory tract.

Gastrointestinal disorders: Gastric pain, abdominal pain, nausea, vomiting, diarrhea.

Hepatobiliary disorders: Cholestatic hepatitis.

Skin and subcutaneous tissue disorders: Urticaria, erythema, rash, pruritus, angioedema, skin reactions, aphthous stomatitis and glossitis. Epidermolysis.

Musculoskeletal and connective tissue disorders: Weakness of the lower limbs.

General disorders and conditions regarding the side of administration: General malaise, generalized edema, asthenia.

Preclinical study results have shown that the drug after acute and chronic dosing for 3 months has no toxic effects in warm-blooded laboratory animals (rodent and non-rodent species – rabbits), including developing organisms.

Potential risks of Libexin® include: hypersensitivity reactions: bronchospasm, skin rash, angioedema; GI tract disorders: dry mouth and throat, transient numbness and loss of sensitivity of the oral mucosa, stomach ache, predisposition to constipations, nausea; nervous system disorders: light sedative effect, fatigue (sedative effect and fatigue are observed at doses exceeding therapeutic, and all symptoms spontaneously resolve within several hours after drug discontinuation).

The study will include only the patients who agree to use adequate contraception measures for the whole study period.

Particular attention in the study will be paid to adverse events on the part of essential organs according to subjective complaints, physical examination, vital signs, laboratory test results, and ECG.

4 SELECTION OF STUDY POPULATION

4.1 Study population

Patients from 18 to 65 years old with dry non-productive cough associated with acute respiratory infection of upper airways. Up to 230 patients will pass screening procedures to randomize 184 patients into one of two study groups at a ratio of 1:1

- Levopront® syrup 30 mg/5 ml — 10 ml t.i.d. for 7 days
- Libexin® 100 mg tablets — 1 tablet t.i.d. for 7 days

4.2 Inclusion Criteria

Subjects should meet the following inclusion criteria to be included into this clinical trial:

1. Signed Informed Consent Form
2. Male or female aged from 18 to 65 (inclusive)
3. Dry non-productive cough as a symptom of acute upper respiratory infection (IDC codes J00-J06)
4. Daytime cough symptom score ≥ 3 points according to the "Six-point daytime and nighttime cough assessment scale"
5. Pre-bronchodilator FEV1 $\geq 70\%$ of the predicted values, post-bronchodilator FEV1 increase of $\leq 12\%$ or ≤ 200 ml compared to the baseline, FEV1/FVC (Tiffeneau index) ≥ 0.7
6. Patient's consent to follow the protocol procedures, including the completion of the patient's diary
7. Patient's consent to use the adequate contraception methods throughout the study period. The adequate birth control methods are as follows:
 - Oral or transdermal contraceptives
 - Condoms or diaphragms (barrier method) with spermicide
 - Intrauterine contraceptive devices

4.3 Exclusion criteria

Subjects with any of the following conditions will be excluded from the study:

1. Hypersensitivity or individual contraindications to Levodropropizine, Prenoxdiazine or additives of the study drug
2. Hereditary fructose intolerance, glucose-lactose malabsorption, lactase deficiency, sucrose-isomaltose deficiency
3. Tuberculosis, bronchial asthma, malignant tumors of lungs or bronchi, COPD, severe respiratory failure (cyanosis, need for respiratory support) or other lung pathology at screening or in history
4. Inhalation anesthesia within 3 months before screening
5. Smoking history of more than 10 pack-years
6. Previous use of cough medicines, ACE inhibitors or amiodarone within 30 days before screening

7. Contraindications or inability to perform spirometry
8. Necessity (in the Investigator's opinion) of prescribing mucolytic agents, expectorants, antibiotics or other medications prohibited by the protocol during the study
9. Excessive mucous excretion which (in the Investigator's opinion) could be a contraindication to prescribing anti-cough medicines; decreased mucociliary function (Kartagener's syndrome, ciliary dyskinesia)
10. Malignant tumors in the past 5 years (except for the basal cell carcinoma)
11. Serious cardiovascular disease at the moment or within 12 months prior to screening, including: Chronic heart failure class III or IV (according to the classification of the New York Heart Association), severe arrhythmias requiring treatment with antiarrhythmic drugs class Ia, Ib, Ic or III, unstable angina, myocardial infarction, heart surgery and coronary arteries, serious valvular heart disease, transient ischemic attack or stroke, uncontrolled hypertension with systolic blood pressure > 180 mmHg and diastolic blood pressure > 110 mmHg, pulmonary embolism or deep vein thrombosis
12. Gastric or duodenal ulcers, gastroesophageal reflux disease within a period of 12 months before screening
13. Systemic autoimmune disorders and connective tissue diseases that require (currently or previously) administration of systemic glucocorticosteroids, cytostatic medications or penicillamine
14. Signs of intensive non-controlled concurrent disease, including disorders of the nervous system, endocrine system, kidneys, liver or gastrointestinal tract, which (in the Investigator's opinion) could prevent the patient's participation in the study
15. History of alcohol or drug abuse at screening or in the past, which results in the inability of the patient to participate in the study at the Investigator's discretion
16. Taking part in another clinical trial or use of study drug within 30 days before screening
17. Pregnant or breast-feeding women or women planning pregnancy during the clinical trial; women of childbearing potential (including not sterilized operatively and in postmenopausal period of less than 2 years), not using appropriate methods of contraception
18. Inability to read or write; unwillingness to understand and follow the procedures of the study protocol; violation of the drug administration regimen or procedure execution that, at the discretion of the Investigator, can impact the results of the study or safety of the patient and interfere his further participation in the study; any other concomitant medical or serious mental conditions that make the patient unsuitable for participation in the clinical study, limit the validity of receiving an informed consent or may affect the patient's ability to participate in the study.

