4.4 Patient Withdrawal After Randomization

The randomization procedure will be performed before laboratory test results are available. In case of significant abnormalities that in the Investigator's opinion interfere with the patient's participation in the study, the patient should be withdrawn from the study.

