5.3 Treatment Compliance

The first dose of the study drug should be taken by patient at the study site under Investigator's control (Visit 1, Day 1). Compliance with guidelines on self-administration of study drugs will be checked by Investigator at Visit 2 and 3 based on account of returned study drug with the diary filled in by the patient. It should be strictly monitored that patient takes 30 mL of the study drug or 3 tablets of reference drug daily.

NB: Patients must take the last dose of the study drug in the evening before Visit 3 (i.e. in the evening of Day 7(±1)) because the **patients should submitted to the examinations requested by the protocol for Day 8 (±1) without having taken the study drug.**

Compliance with the test drug treatment Levopront® will be assessed by the Investigator at Visits 2 and 3. All study sites will be provided with certificated scales. The bottles with syrup will be weighted at the study sites before and after dispensing. The Investigator will measure the difference between initial and final weight. The density of Levopront® is known (indicated in IP documentation), after that calculation of compliance for the syrup will be calculated according to the following formula:

$$\text{Compliance (ml)} = \frac{(\text{m disp.} - \text{m return.})}{\rho \text{ (g/ml)} * V \text{ calc. (ml)}} \times 100\%$$

where m disp. = the m (g) of dispensed syrup, m (g) return. = the number of returned syrup, ρ (g/ml) - density, V (ml) calc. = calculated ml of syrup that the patient had to take from the time of previous visit.

Calculation of compliance for the reference drug will be calculated according to the following formula:

$$\text{Compliance} = (\text{N disp.} - \text{N return.}) / \text{N calc.} \times 100\%$$

where N disp. = the number of dispensed tablets, N return. = the number of returned tablets, N calc. = calculated number of tablets that the patient had to take from the time of previous visit.

Patient compliance for each drug should be similar and be within the interval of 80% to 120%. In case of need patient should be additionally instructed to take the drug.

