6.11 Tests Performed at Local Laboratory

Local laboratory will be used for laboratory tests. Collection, preparation and storage of biological samples will meet requirements of the study site local laboratory.

At baseline, all local laboratories will provide the required certificates and laboratory reference values. Local laboratory is responsible for sending laboratory reports to the Investigator, and for reporting abnormal laboratory values to the Investigator. Investigator should review the laboratory report, all abnormal values should be assessed, signed and dated. Deviations of laboratory values from baseline, reported as AEs should be appropriately reported in the source documentation and in CRF.

Patient randomization is performed before laboratory test results are available. In case of significant abnormality which, at the Investigator's opinion, could interfere with patient's participation in the study or impact interpretation of efficacy or safety parameters, the patient should be withdrawn from the study.

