6.13 Early Withdrawal of Patients from the Study or Discontinuation of Study Treatment

The patient has the right to refuse to take part in the study at any stage without giving reasons.

The patient should be withdrawn from the clinical study if:

- Investigator considers it important from the medical point of view
- Patient withdraws his consent
- Patient does not comply with the study drug dosing regimen or study related procedures
- AE or SAE which may impact safety or well-being of patient
- Infection of lower respiratory tract
- Patient is included into the study with violation of inclusion/exclusion criteria

In the following cases immediate discontinuation of the study drug is required:

- Patient starts administration of another study drug
- Pregnancy in a study subject
- Significant protocol deviations that may impact patient's safety and integrity of the study data
- Use of prohibited drugs

If possible, the Investigator should discuss the need to withdraw the patient with the Medical Monitor or inform about patient withdrawal from the study within 48 hours. The reason for patient withdrawal should be specified in the source documents and in CRF. If a patient discontinues from the study for more than one reason, only the main reason should be specified. If a patient withdraws consent because of AE or SAE, the AE or SAE should be specified as the reason for patient withdrawal.

Besides, the Sponsor may terminate the study at any time. The Investigator has the right to terminate the study at any time for medical or regulatory reasons. Study may only be terminated after mutual consultations between the Investigator and the Sponsor.

If the study is terminated early, all patients should undergo procedures of early termination and all study materials should be returned to the Sponsor or his/her representative.

Follow up of AEs, SAEs and pregnancy ongoing at the time of study termination should be continued per protocol if not agreed otherwise between the Investigator and the Sponsor.

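### Per-protocol membership, which decides the primary non-inferiority test, depends partly on open-label investigator judgement made after randomisation and could differ by arm

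*Protocol*

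**What the plan says.** **Entry criteria.** Exclusion 18 (Protocol 4.3, repeated in the synopsis) includes a "violation of the drug administration regimen or procedure execution that, at the discretion of the Investigator, can impact the results of the study" or the patient's safety. It adds that the violation must "interfere his further participation in the study", which presupposes a patient already enrolled.

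**Withdrawal.** Protocol 6.13 lists as a ground: "Patient is included into the study with violation of inclusion/exclusion criteria". In the same list, non-compliance with dosing or study procedures is a separate ground.

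**Laboratory results.** Protocol 4.4 states: "The randomization procedure will be performed before laboratory test results are available". Its test is whether the investigator thinks an abnormality interferes with participation. Sections 6.11 and 7.1.1 use a wider test, covering abnormalities that "could interfere with patient's participation in the study or impact interpretation of efficacy or safety parameters, the patient should be withdrawn from the study". No numbered eligibility criterion sets a laboratory limit.

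**Dosing compliance.** Protocol 5.3 calculates a percentage for each drug and says: "Patient compliance for each drug should be similar and be within the interval of 80% to 120" per cent. The stated response to a problem is further instruction of the patient.

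**Analysis set.** The PP set is primary (Protocol 9.4.1 and 9.7.1; SAP 5.1 and 7.2.3). It takes randomised patients who completed treatment, have the primary assessment and are judged compliant. Protocol 9.4.1 promises more detail on key deviations in the SAP. SAP 5.1 and 5.4 list none. They provide for a review before database lock and do not say that it is masked to arm or outcome. The trial is open-label (Protocol 3.2, SAP 3).

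**The concern.** A non-inferiority test on a PP set is only as good as the rules that decide who is in it. Here several of those rules are matters of opinion, applied after randomisation by someone who knows the arm and, at visits, records the cough scores.

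Two grounds are worded in terms of the trial's results. Exclusion 18 speaks of violations that can affect the results, and 6.11 and 7.1.1 speak of abnormalities that could affect the interpretation of efficacy. Neither has a threshold. A withdrawn patient leaves the PP set as a non-completer, whatever is later decided about the deviation.

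If the patients lost in this way are non-responders and come more from one arm than the other, the observed difference shifts and the error rate of the primary test changes. The shift can go either way: towards a false claim if Levopront non-responders leave, or towards a lost claim if Libexin non-responders leave.

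**Working it through.** **1. The plan's own sample size.** Inputs from Protocol 9.2: Z values 1.96 and 0.84, 70% response in both arms, margin 20 points, early discontinuation up to 10%.

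n = (1.96 + 0.84)² × (0.7×0.3 + 0.7×0.3) / 0.20² = 7.84 × 0.42 / 0.04 = 82.3 per arm.

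82.3 / 0.9 = 91.5, so 92 per arm and 184 in total. This reproduces. About 83 per arm are therefore expected to be evaluable.

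**2. The decision rule.** Non-inferiority is claimed if the Newcombe hybrid-score lower bound (SAP 7.2.3) exceeds −0.20:

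L = (p_T − p_C) − √[(p_T − l_T)² + (u_C − p_C)²],

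where l_T and u_C are the Wilson lower limit for Levopront and upper limit for Libexin at Z = 1.96.

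**3. How removal changes the error rate.** This is exact enumeration of two independent binomials at the margin (true rates 50% Levopront, 70% Libexin). After each outcome is drawn, k non-responders are removed. The values of k are assumptions; the documents give none.

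| Non-responders removed | 83 per arm | 92 per arm |
|---|---|---|
| None | 2.6% | 2.6% |
| 3 Levopront only | 5.1% | 4.8% |
| 5 Levopront only | 7.3% | 6.9% |
| 3 in each arm | 2.6% | 2.5% |
| 5 in each arm | 2.5% | 2.5% |
| 3 Libexin only | 1.2% | 1.2% |
| 5 Libexin only | 0.8% | 0.8% |

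The 83 column removes patients beyond the 10% allowance. The 92 column treats the removals as part of it. The picture is the same.

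**4. Power in the other direction.** At true rates of 70% in both arms and 92 per arm, power is 0.86. Removing 5 Libexin non-responders alone cuts it to 0.67.

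**5. One data set.**
- 57/92 against 64/92: difference −0.076; l_T = 0.517, u_C = 0.780; L = −0.076 − √(0.102² + 0.085²) = −0.209. Non-inferiority fails.
- Without 3 Levopront non-responders, 57/89 against 64/92: difference −0.055; l_T = 0.537; L = −0.055 − √(0.104² + 0.085²) = −0.189. Non-inferiority passes.

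**6. Counting the removed patients.** If those 3 patients are put back as failures, the counts return to 57/92 and the bound to −0.209. In the same way, the first two Levopront-only rows of the table return to 2.6%. The protocol plans such a missing-as-failure analysis (9.9). The SAP does not carry it forward and plans no replacement of missing efficacy data (SAP 6.1).

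**The case against.** **Exclusion 18 is not the operative route.** This stands. Section 6.13 already withdraws for non-compliance, and the PP definition itself requires compliance. Deleting the clause alone would close nothing.

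**Retroactive ineligibility.** A reader might infer that 6.13 turns a later dosing lapse into an entry violation. The text does not establish this: it refers to a patient who was included in breach of the criteria, which most naturally means status at inclusion. The placement of the clause makes the reading possible but no more, and exclusion 18 also requires interference with further participation.

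**The 80% to 120% range.** A reader might infer that it is a PP rule being bypassed. It is not: 5.3 links it to re-instruction, and SAP 7.3.3 only describes compliance. The defect is that no objective rule defines dosing compliance for the PP set.

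**Laboratory withdrawal and outcome.** Day 1 samples are drawn at Visit 1, and no turnaround time is given. The documents therefore do not show that the investigator would know the cough course when the result is judged. The arm would be known.

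**Safeguards exist.** SAP Table 9.9 repeats the primary endpoint in the ITT set with the same 97.5% bound. The early termination visit repeats all Visit 3 procedures (Protocol 7.5). Withdrawals are discussed with or reported to the Medical Monitor. SAP Table 9.1 gives discontinuation reasons by arm. These reduce the concern without removing it. The claim rests on PP, no rule covers PP and ITT disagreement, the SAP gives patients without Day 8 data no ITT outcome, and Table 9.1 does not give reasons for excluding completers from PP.

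**The magnitude is one-sided.** This also stands. The higher figures need removal from one arm only, of non-responders only, with the truth exactly at the margin.

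**Conclusion.** The concern holds as a weakness in how PP membership is decided. On-study conduct sits among the entry criteria, the laboratory withdrawal test has two wordings and no limit, compliance for PP has no objective definition, and the classification is not stated to be masked in an open-label trial.

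The size is conditional. With 83 per arm at 50% against 70%, removing 3 or 5 Levopront non-responders alone raises false non-inferiority from 2.6% to 5.1% or 7.3%. Balanced removal leaves it at about 2.5% to 2.6%, and removing 5 Libexin non-responders alone lowers it to 0.8%. A reader might take 5% to 7% as the trial's actual error rate. The documents do not support that: they show neither that selective removal happened nor its direction.

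The change is worth making because it is cheap and because PP alone carries the primary conclusion.

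**What to change.** 1. **Protocol 4.3 and synopsis:** take the regimen and procedure violation clause out of the entry criteria. For PP membership only, define dosing compliance by the 80% to 120% percentage already calculated in 5.3, and state whether it applies per visit interval or over the whole treatment period.
2. **SAP 5.1 and 5.4:** have every PP exclusion (dosing, procedure, eligibility, Day 1 pre-dose laboratory) classified before database lock by an existing role without sight of arm or cough scores. Show compliance as a percentage only, since syrup weights or tablet counts reveal the arm. Report exclusions by arm and reason.
3. **SAP 6.1, 7.2.3 and Table 9.9:** carry the missing-as-failure analysis of Protocol 9.9 into the ITT table, and require the PP and ITT conclusions to agree. Step 2 cannot do this alone, because a withdrawn patient still leaves the PP set as a non-completer.
4. **Protocol 4.3, 4.4, 6.11, 6.13 and 7.1.1:** the sponsor must reconcile these passages. No withdrawal rule is proposed here.

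**Cost.** A short masked review step, and a few patients with minor deviations stay in the PP set. Requiring agreement makes the claim somewhat harder to win. Because the first part of the study finished in April 2017, changed entry wording can govern only the second part; the PP classification and ITT analysis can cover all patients. The sample size, visits and safety stopping are unchanged.
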